Follow-up MR or CT imaging will be obtained 2h and 24h post-stimulation (supported by Radiology Dept. research funds). MRI Imaging sequences will include DWI/FLAIR/GRE/PWI/CEMRA and CT imaging sequences will consist of NCCT/CTA/CTP. RAPID image processing software will be applied to the above images to quantify, at the baseline, 2h, and 24h time-points: 1) Ischemic Core volume, 2) Perfusion lesion volume, and 3) Penumbra volume (perfusion volume - core volume). From these values, the following measures will be constructed: 1) Early penumbra preservation: Volume of baseline penumbra tissue not progressing to ischemic core at 2h; 2) Penumbral salvage: Volume of baseline penumbra tissue not progressing to ischemic core at 24h; 3) Early collateral flow enhancement: Perfusion lesion volume at baseline – Perfusion lesion volume at 2h; 4) Sustained collateral flow enhancement: Perfusion lesion volume at baseline – Perfusion lesion volume at 24h; 5) Early infarct growth: Ischemic core lesion volume at 2h – Ischemic core lesion volume at baseline; and 6) Final infarct growth: Ischemic core lesion volume at 24h – Ischemic core lesion volume at baseline. Additional location and extent of ischemic injury at baseline, 2h, and 24h will be rated using the MRI ASPECTS scoring system, with regions considered involved if diffusion restriction is present in more than 20% of the region or CT ASCPETS.^{54,55} In patients receiving MRI, location and extent of FVH and GVH will be rated using the FVH-modified ASPECTS and GVH modified ASPECTS scales.⁵⁶

D.6.10 Adverse Events

D.6.10.1 Serious Adverse Events (SAEs)

All serious adverse events occurring during the 90 days of study participation will be recorded. A serious adverse event is any adverse event that is fatal, is life-threatening, is permanently or substantially disabling, requires or prolongs hospitalization, or requires medical or surgical intervention to prevent one of the above outcomes.¹⁹

D.6.10.2 Symptomatic intracranial hemorrhage

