The trial will be monitored by an Independent Data and Safety Monitoring Board (DSMB). [name] from department of neurorehabilitation will lead the DSMB. DSMB will assess for the causal relationship of the serious adverse event to the study treatment as definite, probable, possible, unlikely, or unrelated.

DSMB will meet at the completion of each dose tier, review all safety data, and determine whether the study will proceed to the next dose tier. DSMB deliberations will be guided by: 1) a formal stopping/escalation rule, based on the occurrence of the lead safety endpoint, symptomatic intracranial hemorrhage (SICH), and 2) The DSMB members' clinical judgement upon review of all other safety outcomes. In addition, DSMB will monitor separately the patients who enroll in the study with a stroke scale 0-3 during the study as they are treated to determine if they have an increase in NIHSS of 2 or more or which is disabling.

Furthermore, Food and Drug Administration (FDA) will be notified if there is one occurrence of SICH prior to repeating the tier or escalating to a higher tier.

E. 2. Statistical Design and Analyses Plan

E.2.1. Sample size

The study sample size derives from the use of the 3+3, rule-based, modified Fibonacci, dose escalation design, with 3:1 randomization to active treatment vs sham control. There will be 6 dose tiers, reflecting increasing intensity and duration of stimulation (Figure 7). The 3+3 study design (3 patients and 1 sham) with 6 dose tiers yields a sample size of at least 24 and potentially up to 48. The 3+3 design is the classical approach to dose escalation in first-in-human studies.^{57,58} While newer, adaptive designs for dose escalation trials have been developed, they are more complex and have limited advantages when major toxicities are not expected.⁵⁹ Therefore, the rule-based, 3+3 design remains the dominantly employed approach in current dose-escalation studies. We will take every step to avoid missing data by scheduling of the follow-up visits early in visit time windows and readiness to travel to the patient's location to perform needed assessments. Should any missing data occur, primary analyses will be performed using multiple imputation, with sensitivity analyses including complete case and worst possible outcome analyses.⁶⁰

E.2.2. Baseline characteristics

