For the final statistical analysis of the primary SICH safety endpoint, a chi-square test will be used to detect differences in the rate of SICH between the active treatment and sham patients and higher and lower dose tiers. The treatment will be considered to have exhibited adequate safety in the current trial to proceed to future, larger, pivotal efficacy trials if tDCS results in lower or equivalent rates of SICH compared to sham.

E.2.3.3. Secondary Safety Endpoints Analysis

In secondary safety endpoint analyses, the following will be compared between the active treatment and sham patients, and between higher and lower dose tiers, using chi-squared tests: **1) Asymptomatic ICH by 24h** (intracranial hemorrhage not associated with NIHSS worsening ≥ 4); **2) Early neurologic deterioration** (worsening ≥ 4 on NIHSS during the 24-hour period after stimulation, with or without intracranial hemorrhage); **3) All-cause mortality at day 90 (mRS);** and **4) All serious adverse events.**

E.3.3. Tolerability Endpoint Analysis

The lead tolerability endpoint is completion of the protocol-assigned stimulation treatment without early cessation due to cutaneous, neurologic, nociceptive or other adverse effects. Experience with tDCS in post-stroke patients indicates only infrequent cutaneous (itching, tingling) adverse effects are likely to occur. Accordingly, for the current study, a patient will be considered to have tolerated the procedure if at least 75% of the stimulus period was completed. The treatment will be considered generally tolerable if, among all enrolled patients, tolerated procedures are achieved in $\geq 90\%$ of patients, assessed with a one-sided p value of 0.025. Secondary tolerability endpoints will be the

rate and severity of cutaneous, neurological, and pain items of the technician-filled (Figure 7) and patient-filled tolerability forms ⁴⁹, descriptively compared between active treatment and sham patients, and between higher and lower dose tiers.

E.3.4. Feasibility Endpoint Analysis (Specific Aim 2)

A time-motion analysis and mock run-throughs will be conducted prior to first enrollment. Nonetheless, it is anticipated that processes to optimize rapid placement of the cap and electrodes will continue to improve with experience gained from initially enrolled patients. The predefined success threshold for feasibility will be median time from randomization to tDCS initiation \leq 10 minutes in the last 10 enrolled patients.

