E.3.5. Exploratory Efficacy Endpoints Analysis (Specific Aim 3)

E.3.5.1. Exploratory Imaging Biomarker Efficacy Endpoints

This study is underpowered to definitively determine efficacy, so all imaging efficacy analyses will be purely exploratory and descriptive. Imaging biomarker efficacy endpoints will be characterized in the active and sham patients, and in higher and lower dose tiers, using means and 95% confidence intervals. The six imaging efficacy endpoints of greatest interest that will be explored are: early and late penumbral salvage, early and late collateral flow enhancement, and early and late infarct growth.

E.3.5.2. Exploratory Clinical Efficacy Endpoints

This study is underpowered to definitively determine efficacy, so all clinical efficacy analyses will be purely exploratory and descriptive. Four clinical outcome measures were selected based on their reliability, familiarity to the neurologic community, and adaptability for use in patients who have had a stroke. These endpoints are: the modified Rankin Scale (mRS), a rating of global disability; the Barthel Index (BI), a measure of instrumental activities of daily living; the National Institutes of Health Stroke Scale (NIHSS), a measure of neurologic deficit severity; and the EuroQol (EQ-5D), an assessment of health-related quality of life; and AMC Linear Disability Scale, a granular degree of disability.

Clinical efficacy endpoints will be characterized in the active and sham patients, and in higher and lower dose tiers. Early course clinical efficacy endpoints of greatest interest that will be explored are: **1)** Normalized change in neurologic deficit from baseline to 24h (normalized delta NIHSS – linear variable, analyzed with means and 95% CIs; and **2)** Degree of neurologic deficit at 24h (NIHSS – quasi-linear variable, analyzed with means and 95% CIs). Final outcome clinical efficacy endpoints of greatest interest that will be explored are: **1)** Degree of disability at 90 days, assessed across all 7 levels of the modified Rankin Scale – ordinal variable, analyzed with medians (IQRs) and means (95% CIs); **2)** Functional independence (mRS 0-2) at 90 days – binary variable, analyzed with rates and 95% CIs; **3)** Granular degree of disability at 90 days (AMC Linear Disability Scale) – linear variable, analyzed with means and 95% CIs; and **4)** Health-related quality of life (EQ-5D) – linear variable, analyzed with means and 95% CIs.

References:

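### The missing-data rule does not except death, so day-90 EQ-5D and AMC scores of patients who die could be imputed from survivors

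*Combined protocol and SAP*

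**What the plan says.** The rule is at the end of E.2.1 (Sample size): "Should any missing data occur, primary analyses will be performed using multiple imputation", followed in the same sentence by "with sensitivity analyses including complete case and worst possible outcome analyses". Neither E.2.1 nor any other section says whether a death counts as missing data.

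The schedule in D.6.1 and the visit list in D.6.8 place EQ-5D, the AMC scale and the Barthel Index at day 90 only. E.3.5.2 then treats the 90-day outcomes as follows:

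- The mRS is "assessed across all 7 levels of the modified Rankin Scale". E.2.3.3 reads day-90 mortality from the mRS, so one of those levels is death.
- The AMC scale and EQ-5D are each summarised by means and 95% confidence intervals, for active and sham patients and for higher and lower tiers. No value is given for a patient who has died.
- The Barthel Index is named as an outcome measure but is left off the list of final outcomes of greatest interest and has no stated summary.

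E.3.5.2 calls all clinical efficacy analyses exploratory and descriptive. D.6.10.2 says that the decision on further development will weigh all the outcome measures.

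**The concern.** A dead patient has no EQ-5D or AMC score. That is a different situation from a living patient whose visit was missed, and the plan does not separate the two.

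Because neither scale has an earlier measurement, every observed value comes from a survivor, and an imputation model fitted to those values can only give a dead patient a survivor-like score. The complete-case analysis drops the deaths. The worst-possible-outcome analysis would score them poorly, but it would give the same score to a living patient lost to follow-up.

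If mortality differs between arms or tiers, the EQ-5D and AMC means would then fail to reflect it. These scales are named in Specific Aim III, and the trial is meant to identify promising dose regimens, so their means by arm and tier will be read even though they are exploratory.

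**Working it through.** **1. Sample size from the plan.** E.2.1 describes "The 3+3 study design (3 patients and 1 sham) with 6 dose tiers" and says that it "yields a sample size of at least 24 and potentially up to 48".

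- Minimum: 6 × (3 + 1) = 24, which is 18 active and 6 sham.
- Maximum, with every tier expanded once: 2 × 24 = 48, which is 36 active and 12 sham.

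Both figures reproduce.

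**2. Will the case arise?** The documents give no day-90 death rate, so 10%, 20% and 30% are assumed. The chance of at least one death among 24 is 1 − (1 − p)^24.

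| Assumed mortality | Expected deaths of 24 | Expected deaths of 48 | Chance of at least one death in 24 |
|---|---|---|---|
| 10% | 2.4 | 4.8 | 92% |
| 20% | 4.8 | 9.6 | 99.5% |
| 30% | 7.2 | 14.4 | over 99.9% |

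**3. Effect on the EQ-5D difference.** Let m be the mean among survivors, assumed equal in both arms, and let dA and dS be the death rates on active and sham.

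- Deaths imputed at the survivor mean: difference = m − m = 0, whatever the mortality.
- Death scored as 0: difference = m(1 − dA) − m(1 − dS) = m(dS − dA).

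With m assumed to be 0.5 to 0.7:

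| Active deaths | Sham deaths | Deaths imputed at m | Death scored as 0 |
|---|---|---|---|
| 10% | 10% | 0 | 0 |
| 20% | 10% | 0 | -0.05 to -0.07 |
| 30% | 10% | 0 | -0.10 to -0.14 |
| 30% | 30% | 0 | 0 |

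**4. Direction, with counts at N = 24 and m = 0.6, death scored as 0.**

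- 3 of 18 active and 0 of 6 sham deaths: 0.6 × 15/18 − 0.6 = 0.50 − 0.60 = -0.10.
- 0 of 18 active and 1 of 6 sham deaths: 0.6 − 0.6 × 5/6 = 0.60 − 0.50 = +0.10.
- 3 of 18 active and 1 of 6 sham deaths: 0.50 − 0.50 = 0.

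So the distortion can favour either arm. With 6 sham patients, one death is 1/6, or 17%, of that arm.

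**The case against.** **The rule may not reach these scales.** It speaks of primary analyses, and these endpoints are exploratory. The sentence before it is about scheduling visits early and travelling to patients, which concerns living patients. Part of this stands: the plan never says in terms that a death is treated as missing. But the sentence sets primary against sensitivity analyses, so the more natural reading is the main analysis of each outcome. If the narrower reading is right, EQ-5D and AMC have no rule at all, and the choice would be made after the data are seen. Text is needed either way.

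**A reader might infer that the plan hides harm.** The documents do not support that. Day-90 all-cause mortality is a secondary safety endpoint compared by arm and tier (E.2.3.3). D.6.10.1 says "A serious adverse event is any adverse event that is fatal", and these events are recorded for 90 days. The mRS has a level for death. The DSMB reviews all safety data at each tier. The escalation rule and the primary safety criterion use symptomatic intracranial hemorrhage, not these scales.

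**The worst-possible-outcome analysis already covers deaths.** It does so only if deaths are counted as missing, only as a sensitivity analysis, and without separating death from loss to follow-up.

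**The figures assume every death is imputed at the survivor mean.** This is a fair limit. The plan specifies multiple imputation but gives no model. A model using baseline NIHSS or the day-4 and day-30 mRS could give lower values to patients who die, and the distortion would be smaller.

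**The Barthel Index.** A reader might extend the point to a biased Barthel result. With no stated summary, there is no planned analysis to which that bias can be traced.

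**Conclusion.** The point holds for EQ-5D and the AMC scale. As written, the main analysis rule makes no exception for death, and following it literally gives dead patients values drawn from survivors. The consequence is confined to exploratory scales that nonetheless feed the development decision.

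Under the assumptions above, the part of the EQ-5D difference that could be lost is 0.05 to 0.14. It is zero if mortality is equal, and its sign depends on which arm has more deaths. The mortality rates, the survivor mean, its equality across arms and imputation at that mean are all assumptions, so the figures illustrate scale and do not predict the result. No corresponding AMC figure can be given, because the documents do not state its range.

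**What to change.** In E.2.1 and E.3.5.2:

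- State that death is not missing data and is excluded from imputation. Impute only for patients known or presumed alive at day 90.
- In the main summary, give deaths a prespecified value: 0 on the EQ-5D index, as the value for death, and the worst end of the AMC scale. Do the same for the Barthel Index if it is to be summarised. The EQ-5D scoring and the AMC range need stating for this to be unambiguous.
- Show medians alongside the means, and survivors-only summaries labelled as such, next to mortality by arm.

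The cost is a few sentences, with no change to design, sample size or data collection. The drawback is that the means then combine death and disability, which is why the medians and survivors-only summaries should accompany them.

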The demographic and baseline clinical characteristics of the study population will be delineated with standard descriptive statistics. Categorical variables describing the clinical history, examination findings, and initial treatment will be summarized by

frequencies. Continuous variables such as vital signs, laboratory results, and time variables will be characterized by means, standard deviations, and 95% confidence intervals (CI). Ordinal and non-normally distributed variables (such as the NIHSS) will be characterized by medians and interquartile ranges. Baseline characteristics will be compared between the tDCS stimulation group with sham group to assess covariate balance. Wilcoxon Rank-Sum tests will be used for continuous or ordinal variables; Fisher's exact tests and chi-square tests will be used for grouped or nominal categorical variables.

E.2.3. Safety and Tolerability (Specific Aim 1)

E.2.3.1 Dose Escalation

The study Data and Safety Monitoring Board (DSMB) will meet at the completion of each dose tier, review all safety data, and determine whether the study will proceed to the next dose tier. DSMB deliberations will be guided by: 1) a formal stopping/escalation rule, based on the occurrence of the lead safety endpoint, symptomatic intracranial hemorrhage (SICH), and 2) The DSMB members' clinical judgement upon review of all other safety outcomes. The formal dose escalation rule uses SICH frequency to gate the occurrence and pace of escalation through the 6 dose tiers. If no SICH occurs in the 3 active patients at a dose tier, enrollment may escalate to the next dose tier. If one SICH occurs, 3 more active (and 1 more control) patient will be enrolled at that dose tier before escalation. If 2 SICHs occur at a dose tier, further study enrollment is held until detailed review by the DSMB (Fig 6). In addition, whenever the formal SICH criteria for dose escalation has been met, the DSMB will formally meet, review the SICH data and all other safety data, and advice regarding proceeding to the next tier, continuing at the current tier, or placing the study on hold.

E.2.3.2. Primary Safety Endpoint Analysis

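### Multiple imputation is the primary method for missing data and SICH is not exempt, so one patient with unknown SICH status could let an unspecified imputation model decide the safety criterion

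*Combined protocol and SAP*

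**What the plan says.** Section E.2.1 of the combined protocol and SAP holds the only missing-data rule: if any data are missing, "primary analyses will be performed using multiple imputation", "with sensitivity analyses including complete case and worst possible outcome analyses". It gives no imputation model, covariates, number of imputations or pooling rule, and does not say which analysis governs if they disagree.

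The same section fixes the size of the trial. Six tiers of three active patients and one sham patient, each expandable once, give a design that "yields a sample size of at least 24 and potentially up to 48". Section E.2.3.1 sets the expansion rule: after one SICH, "3 more active (and 1 more control) patient will be enrolled at that dose tier before escalation".

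Sections D.6.10.2 and E.2.3.2 make SICH the primary safety endpoint. It requires an NIHSS rise of at least 4 points within 24 hours together with a qualifying hemorrhage. The treatment counts as safe enough to take forward "if tDCS results in lower or equivalent rates of SICH compared to sham". No margin or confidence bound is attached.

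**The concern.** A comparison of two raw rates, one based on 6 or 7 patients, can turn on a single event. If a SICH status is unknown, the primary analysis replaces it with model draws, and the plan leaves that model open. When no sham patient has an event, a logistic imputation model containing arm is separated: the data cannot estimate the sham log-odds, and the draws reflect the software rather than the patients. The formal safety conclusion, which informs the move to larger trials, could then rest on a default nobody chose. The planned complete-case analysis would expose such a discrepancy, but only as a sensitivity analysis with no stated authority over the primary result.

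**Working it through.** **The plan's own figure.** 6 × (3 + 1) = 24 and 6 × 2 × (3 + 1) = 48, matching the stated range. This implies 18 to 36 active and 6 to 12 sham patients. Sham numbers rise above 6 only as tiers expand after a SICH.

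**How likely is an empty sham cell?** The documents give no SICH rate, so rates p of 1%, 2%, 5% and 10% are assumed. The chance of no event in 6 sham patients is (1 − p)^6 = 94%, 89%, 74% and 53%.

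**Reading of the criterion.** With no margin given, it is taken as active rate ≤ sham rate.

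**Case 1: one active SICH, one sham status missing.** One active SICH expands a tier, so the completed trial has 21 active and 7 sham patients. Observed: 1/21 = 4.8% active, 0/6 = 0% sham, one sham unknown. On observed data the criterion is not met.

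If q is the imputed event probability, the expected sham rate is q/7. With m imputations, k of which give an event, the pooled sham rate is (k/m)/7. The criterion is met when (k/m)/7 ≥ 1/21, that is k/m ≥ 1/3. With m = 20 (assumed) that means k ≥ 7, and k is binomial(20, q).

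| Imputation model | q | Sham rate q/7 | Chance criterion is met |
|---|---|---|---|
| Unpenalised logistic on arm | 0.50 | 7.1% | 94% |
| Sham arm only, Beta(0.5, 0.5) prior | 0.5/7 = 0.071 | 1.0% | under 0.1% |
| Sham arm only, Beta(1, 1) prior | 1/8 = 0.125 | 1.8% | 0.8% |
| Pooled over arms | 1/27 = 0.037 | 0.5% | under 0.1% |

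In the first row the fitted sham intercept is −21.6 with a standard error of about 11,900. Normal draws that wide give probabilities that are nearly all 0 or 1, averaging one half, although 0/6 was observed.

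**Case 2: no SICH observed, one active status missing.** No tier expands. Observed: 0/17 active plus one unknown, 0/6 sham. On observed data the criterion is met (0% against 0%). Any imputed event makes the pooled active rate positive against 0% sham, so the chance that the criterion fails with m = 20 is 1 − (1 − q)^20.

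| Imputation model | q | Active rate q/18 | Chance criterion fails |
|---|---|---|---|
| Unpenalised logistic on arm | 0.50 | 2.8% | about 100% |
| Active arm only, Beta(1, 1) prior | 1/19 = 0.053 | 0.3% | 66% |
| Active arm only, Beta(0.5, 0.5) prior | 0.5/18 = 0.028 | 0.2% | 43% |
| Pooled, Beta(0.5, 0.5) prior | 0.5/24 = 0.021 | 0.1% | 34% |

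**The planned worst-outcome analysis.** E.2.1 does not say to which arm it applies. Applied to both arms in Case 1 it gives 1/21 = 4.8% against 1/7 = 14.3%, so the criterion is met. It is not reliably the cautious analysis.

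**The case against.** The strongest reply is that SICH status will almost never be missing. A missed 24-hour scan might be read as a missing SICH status, but the definition does not support that: a patient with recorded NIHSS and no rise of 4 points is a non-event whatever a scan would show. NIHSS is taken after each stimulation cycle, at 2 hours and at 24 hours. Suspected worsening calls for immediate imaging, and the core lab reviews every additional scan in patients who worsen by 4 points. Status is unknown mainly when a patient worsens or dies unscanned, or when both NIHSS and imaging are absent. This stands.

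It is also true that the change from not met to met (Case 1) needs an unpenalised logistic model, which the plan does not prescribe, and that a standard error near 12,000 is a visible fitting failure. Case 2 does not need a poor model, although its error is in the cautious direction.

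A reader might infer that imputation would necessarily hide bleeds because it assumes missingness unrelated to outcome. That overstates it. Standard multiple imputation assumes missing at random given the observed data, which here could include 2-hour NIHSS and imaging. The concern remains if the model omits them, or if missingness depends on the bleed beyond them.

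Consequences are limited too. Escalation under E.2.3.1 uses SICH occurrence with DSMB review and does not mention imputation, and D.6.10.2 bases further development on all outcomes together. None of this supplies the missing rule for the formal criterion in E.2.3.2.

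**Conclusion.** The concern holds as a conditional one. If a SICH status is missing, the primary analysis leaves the safety criterion to an unstated model. In Case 1 the sham rate after imputation ranges from 0.5% to 7.1% against 4.8% active, so the model choice settles the answer. In Case 2 a met criterion becomes unmet in 34% to about 100% of runs.

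This rests on assumptions the documents do not supply: few SICH events, one unknown status, 20 imputations, and a criterion read as active rate no higher than sham. A reader might infer that imputation will break down or reverse the safety conclusion. The documents do not support that: they give neither a SICH rate nor a missing-data rate nor a model, and nothing changes if every status is known. The point is worth correcting before analysis but does not undermine the trial's conduct. The marginless comparison itself is a separate weakness.

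**What to change.** In E.2.1, exempt SICH and the other binary safety endpoints from multiple imputation, and keep it for the 90-day scale scores. Make observed adjudicated events the primary analysis, and state that a patient with recorded NIHSS and no rise of 4 or more is a SICH non-event. Report best-case and worst-case bounds by arm, including the combination least favourable to the device (active unknowns as events, sham unknowns as non-events), and state whether the E.2.3.2 criterion holds across them. In Case 1 the bounds run from 1/21 against 1/7 (met) to 1/21 against 0/7 (not met). In Case 2 they run from 0/18 against 0/6 (met) to 1/18 against 0/6 (not met).

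Counting only active unknowns as events should be a bound, not the primary analysis. It is one-sided, is not what E.2.1 now plans, and in Case 2 would by itself make the criterion fail.

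The cost is a few sentences, with no extra patients or procedures. The downside is that if a status is missing, the safety conclusion may have to be reported as not robust.
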